1 GLOSSARY OF TERMS

Names of test product(s)	Throughout this document, test product(s) will be referred to as TOTAL30® soft contact lenses (TOTAL30) [REDACTED]
Name of Comparator Product(s)	Throughout this document, comparator product(s) will be referred to as ACUVUE OASYS® with HYDRACLEAR® PLUS contact lenses (AOHP) [REDACTED]
Adverse Device Effect (ADE)	Adverse event related to the use of an investigational medical device (investigational product) or control product. Note: This definition includes adverse events resulting from insufficient or inadequate instructions for use, deployment, implantation, installation, or operation; any malfunction; and use error or intentional misuse of the investigational medical device (investigational product) or control product.
Adverse Event (AE)	Untoward medical occurrence, unintended disease or injury, or untoward clinical signs (including abnormal laboratory findings) in subjects, users or other persons, whether or not related to the investigational medical device (investigational product). Note: This definition includes events related to the investigational medical device, comparator, or the procedures involved. For users or other persons, this definition is restricted to events related to the use of investigational medical devices (investigational product) or control product. Requirements for reporting Adverse Events in the study can be found in Section 11.

Clinical Investigation Plan (CIP)	
The document(s) stating the rationale, objectives, design, and prespecified analysis, methodology, organization, monitoring, conduct, and record-keeping of the clinical investigation.
 
Note: The protocol and other documents referenced in the protocol (for example, the Statistical Analysis Plan, the Manual of Procedures, the Deviations and Evaluability Plan, and the Protocol Monitoring Plan) comprise the CIP.

Clinical Investigation Report (CIR) / Clinical Study Report	
The document describing the design, execution, statistical analysis, and results of a clinical investigation. The Clinical Investigation Report is synonymous with the Clinical Study Report.

Device Deficiency	
Inadequacy of a medical device with respect to its identity, quality, durability, reliability, usability, safety, or performance.
 
Note: This definition includes malfunctions, use errors, and inadequacy in the information supplied by the manufacturer including labelling.
 
Requirements for reporting Device Deficiencies in the study can be found in Section 11.

Enrolled Subject	
Any subject who signs an informed consent form for participation in the study.

Point of Enrollment	
The time at which, following recruitment and before any clinical investigation-related procedures are undertaken, a subject signs and dates the informed consent form.

Interventional Clinical Trial	
A pre- or postmarket clinical investigation where the assignment of a subject to a particular medical device is decided in advance by a clinical investigation plan, or diagnostic or monitoring procedures requested in the CIP are in addition to those available as normal clinical practice and burden the subject.

Investigational Product	A preventative (vaccine), a therapeutic (drug or biologic), device, diagnostic, or palliative used as a test or comparator product in a clinical trial, including a product with a marketing authorization when used or assembled (formulated or packaged) in a way different from the authorized form, or when used for an unauthorized indication, or when used to gain further information about the authorized form.
Malfunction	Failure of an investigational medical device to perform in accordance with its intended purpose when used in accordance with the instructions for use or clinical investigation plan (CIP).
Nonserious Adverse Event	Adverse event that does not meet the criteria for a serious adverse event.
Product Complaint	Any oral, electronic, or written communication that alleges deficiencies related to the identity (labeling), quality, durability, reliability, safety, effectiveness, or performance of a marketed product, including failure of the product, labeling, or packaging to meet specifications, whether or not the product is related to or caused the alleged deficiency. A complaint may allege that an adverse event or medical device malfunction has occurred.
Randomized Subject	Any subject who is assigned a randomized treatment.
Serious Adverse Device Effect (SADE)	Adverse device effect that has resulted in any of the consequences characteristic of a serious adverse event.

Serious Adverse Event (SAE)	
Adverse event that led to any of the following:
 
• Death.• A serious deterioration in the health of the subject, users or other persons as defined by one or more of the following:
a) a life-threatening illness or injury Note: Life-threatening means that the individual was at immediate risk of death from the event as it occurred, i.e., it does not include an event which hypothetically might have caused death had it occurred in a more severe form.b) any potentially sight-threatening event or permanent impairment to a body structure or a body function including chronic diseases.c) inpatient hospitalization or prolonged hospitalization. Note: Planned hospitalization for a preexisting condition, without serious deterioration in health, is not considered a serious adverse event. In general, hospitalization signifies that the individual remained at the hospital or emergency ward for observation and/or treatment (usually involving an overnight stay) that would not have been appropriate in the physician's office or an outpatient setting. Complications that occur during hospitalization are adverse events. If a complication prolongs hospitalization or fulfills any other serious criteria, the event is serious. When in doubt as to whether "hospitalization" occurred, the event should be considered serious.d) a medical or surgical intervention to prevent a) or b).e) any indirect harm as a consequence of incorrect diagnostic test results when used within manufacturer's instructions for use.
-----------------------------	---

	
• Fetal distress, fetal death, congenital abnormality or birth defect including physical or mental impairment. 
Note: Planned hospitalization for a preexisting condition, or a procedure required by the CIP, without serious deterioration in health, is not considered a serious adverse event.
 
Refer to Section 11 for additional SAEs.

Serious Health Threat	
Signal from any adverse event or device deficiency that indicates an imminent risk of death or a serious deterioration in the health in subjects, users, or other persons, and that requires prompt remedial action for other subjects, users, or other persons.
 
Note: This would include events that are of significant and unexpected nature such that they become alarming as a potential serious health hazard or possibility of multiple deaths occurring at short intervals.

Study Start	
The start of the study is considered to coincide with the enrollment of the first patient.

Study Completion	
The completion of the study is considered to coincide with the database lock or the decision to terminate the trial, whichever is later.

Use Error	
User action or lack of user action while using the medical device that leads to a different result than that intended by the manufacturer or expected by the user.
 
Note:
 
a) Use error includes the inability of the user to complete a task.b) Use errors can result from a mismatch between the characteristics of the user, user interface, task, or use environment.c) Users might be aware or unaware that a use error has occurred.d) An unexpected physiological response of the patient is not by itself considered a use error.e) A malfunction of a medical device that causes an unexpected result is not considered a use error.”
-----------	--

2 LIST OF ACRONYMS AND ABBREVIATIONS

[figure not shown]
[figure not shown]
[figure not shown]
Table 2–1 List of Acronyms and Abbreviations Used in This Protocol

[figure not shown]

Abbreviation	Definition
ADE	Adverse device effect
AE	Adverse event
AOHP soft contact lens or AOHP	ACUVUE OASYS with HYDRACLEAR PLUS (AOHP) (senofilcon A) (██████████)
AOS	Advanced Ophthalmic Systems
BCVA	Best corrected visual acuity
CE	Conformité Européenne
CFR	Code of Federal Regulations
CIP	Clinical Investigation Plan
CIR	Clinical Investigation Report
██████████	██
COL	Clinical operations lead
CRF	Case report form
CSM	Clinical site manager
CTT	Clinical trial team
D	Diopter(s)
eCRF	Electronic case report form
EDC	Electronic data capture
FDA	US Food and Drug Administration
GCP	Good Clinical Practice
GPCMS	Global Product Complaint Management System
hr	Hour
IB	Investigator’s brochure
ICF	Informed consent form
IEC	Independent ethics committee
IFU	Instructions for use
IP	Investigational product
IRB	Institutional review board
ISO	International Organization for Standardization
██████████	██
logMAR	Logarithm of the minimum angle of resolution
mm	Millimeter
MOP	Manual of procedures
N/A	Not applicable
OD	Right eye
OS	Left eye
SADE	Serious adverse device effect
SAE	Serious adverse event
SD	Standard deviation

Abbreviation	Definition
SLE	Slit lamp examination
SOP	Standard operating procedure
TOTAL30 soft contact lens or TOTAL30	TOTAL30 soft contact lenses [REDACTED]
UK	United Kingdom
US / USA	United States of America
USV	Unscheduled visit
VA	Visual acuity
[REDACTED]	[REDACTED]

3 PROTOCOL SUMMARY

Investigational product type	Device
Study type	Interventional
Investigational products	Test Product: TOTAL30 soft contact lenses (TOTAL30) [REDACTED] Comparator Product: ACUVUE OASYS with HYDRACLEAR PLUS soft contact lenses (AOHP) [REDACTED]
Purpose and Scientific Rationale for the Study	The overall objective of this clinical study is to describe the clinical performance of the TOTAL30 soft contact lens compared to the AOHP soft contact lens in a daily wear modality.
Objective(s)	The primary objective is to evaluate visual acuity of the TOTAL30 soft contact lens and the AOHP soft contact lens. [REDACTED] [REDACTED] [REDACTED]
Endpoint(s)	Primary Effectiveness 
Distance VA (logMAR) with study lenses [REDACTED]

	
	
Safety
 
• Adverse events• Biomicroscopy findings• Device deficiencies
	
Assessment(s)	
Effectiveness
 
• Distance VA (logMAR) with study lenses
	

	 
Safety
 
• Adverse events• Biomicroscopy• Device deficiencies 
Study Design	
This will be a prospective, randomized, , , bilateral crossover, controlled, subject-masked, daily wear clinical study.
 
Subjects will be expected to attend 3 visits. The total duration of a subject's participation in the study will be approximately 1.5 months. Subjects will be expected to wear their study contact lenses at least 5 days per week and at least 8 hours per day. On visits 2 and 3, subjects will be expected to wear the study lenses at least 6 hours prior to the study visit and the visit is to take place within ± 2 hours of baseline visit time. 
  

[figure not shown]
Subject population	Volunteer subjects aged ≥ 18 years who are any habitual spherical soft contact lens wearers, have at least 3 months of contact lens wearing experience, and who would be willing to wear the study lenses for at least 5 days per week and at least 8 hours per day. Pregnant and breastfeeding women are excluded for this study. Planned number of subjects enrolled/consented: ~36 Planned number of completed subjects: 32 [REDACTED] [REDACTED]
Sites and Locations	Planned number of clinical sites: 1 Planned locations (initial list of locations, which may change during start up or conduct according to study needs): UK
Key inclusion criteria (See Section 8.1 for a complete list of inclusion criteria)	
• Current wearers of any commercial spherical soft contact lenses with at least 3 months wearing experience, who would be willing to wear the study lenses for a minimum wearing time of 5 days per week and 8 hours per day.• Able to wear contact lenses within a range of sphere power from -1.00 D to -6.00 D (0.25 D steps) and subject willing and able to wear the study lenses for the full duration of the study.• Willing to NOT use rewetting/lubricating drops at any time during the study.
Key exclusion criteria (See Section 8.2 for a complete list of exclusion criteria)	
• Participation of the subject in a clinical trial within the previous 14 days or currently enrolled in any clinical trial.• Habitual AOHP contact lens wearers (in the past 3 months)• Monovision wear during the study.
Data analysis and sample size justification	Planned Analysis To address the primary objective, descriptive statistics (number of observations, mean, standard deviation, median, minimum, maximum) for visual acuity, collected for each eye, on the logMAR scale will be provided. No inferential testing will be conducted.

	
Sample Size Justification
 
Given the feasibility nature of this study, sample size calculation is not relevant.

Associated materials
	
AOSEPT PLUS with HydraGlyde Cleaning & Disinfecting Solution will be used for daily cleaning and disinfection.
 
Lubrication/rewetting drops will not be permitted during this study.

Table 3–1 Schedule of Study Procedures and Assessments

Procedure/ Assessment	Pre-screening	LENS PAIR 1		LENS PAIR 2		Early Exit	USV
		Visit 1 Screen/Baseline/ Dispense Pair 1	Visit 2 Follow-up Pair 1 [§] / Dispense Pair 2	Visit 3 Follow-up Pair 2 [§] /Exit			
		Visit Window ^Ω		Visit Window ^Ω			
		Day 1	AOHP = [Day 14 (-3/+7 days)] TOTAL30 = [Day 28 (-3/+7 days)]	AOHP = [Day 14 (-3/+7 days)] TOTAL30 = [Day 28 (-3/+7 days)]			
Pre-Screening Consent	X						
Informed Consent		X					
Demographics		X					
Medical History*		X	X		X	X	X
Pregnancy Form*			(X)		(X)	(X)	X
Concomitant Medications*		X	X		X	X	X
Inclusion/Exclusion		X					
Habitual (lens brand, lens power*, lens care)		X					
Keratometry readings (OD, OS)		X					
Manifest refraction*		X	(X)		(X)	(X)	(X)
BCVA* (OD, OS, logMAR distance with manifest refraction)		X	(X)		(X)	(X)	(X)
Biomicroscopy		X	X		X	X	(X)
Randomization		X					
VA w/ study lenses, (OD, OS, logMAR distance)		X (optimization and baseline measurements for both study lens types)	X (lens pair 1)		X (lens pair 2)	X	X
Slit-lamp photo/video of study lenses*		(X)	(X)		(X)	(X)	(X)
Dispense (provide) study lenses		X					(X)

Procedure/ Assessment	Pre-screening	LENS PAIR 1		LENS PAIR 2		Early Exit	USV
		Visit 1 Screen/Baseline/ Dispense Pair 1	Visit 2 Follow-up Pair 1 ^S / Dispense Pair 2	Visit 3 Follow-up Pair 2 ^S /Exit			
		Visit Window ^Ω		Visit Window ^Ω			
		Day 1	AOHP = [Day 14 (-3/+7 days)] TOTAL30 = [Day 28 (-3/+7 days)]	AOHP = [Day 14 (-3/+7 days)] TOTAL30 = [Day 28 (-3/+7 days)]			
Subjective VAS questionnaire		X (baseline measurements for both study lens)	X (lens pair 1)	X (lens pair 2)		X	(X)

AEs		X	X	X	X	X
Device deficiencies		X	X	X	X	X
Exit Form		(X)	(X)	X	X	(X)

(X) Assessment performed as necessary, eg, decrease of VA by 2 lines or more with investigational product (IP)

USV = Unscheduled Visit

* Source only

^S Subjects are required to wear the study lenses at least 6 hrs on the day of follow-up visits prior to the visit. Follow-up visit time to be within ±2 hours of baseline visit time.

^Ω Visit 2 and 3 visit window and exposure period is dependent on the randomized treatment sequence. AOHP exposure period is to be 14 days (-3/+7 days) and TOTAL30 exposure period is to be 28 days (-3/+7 days)

4 PROTOCOL AMENDMENTS

Modification of the protocol is prohibited without prior written agreement in the form of a protocol amendment. All amendments must be created by the study sponsor and must be approved by the IRB/IEC and global and regional Health Authorities, as applicable, prior to implementation except when required to mitigate immediate safety risks or when the changes involve only logistical or administrative revisions.

Amendments may necessitate that the informed consent and other study-related material be revised. If the consent form is revised, all subjects currently enrolled in the study must sign the approved, revised informed consent (re-consent), as required by the IRB/IEC.

5 INTRODUCTION

5.1 Rationale and Background

Daily wear contact lenses are worn during waking hours, often for a full day and then removed for cleaning and disinfection prior to reinsertion the following day. Frequent replacement daily wear contact lenses are replaced according to the product package insert/IFU provided by the contact lens manufacturer.

New silicone hydrogel materials continue to be developed, possessing unique material properties and superior oxygen transmissibility over contact lenses made with conventional hydrogel materials. A new lens, known as the TOTAL30 contact lens, has been developed in an effort to maintain sustained performance by providing an inherently wetttable core material with a water gradient surface. The new silicone hydrogel lens has been designed to provide favorable performance for daily wear with 1-month replacement.

In this clinical study, the clinical performance of the TOTAL30 contact lens will be assessed and the TOTAL30 contact lens will be compared to the AOHP contact lens in a crossover design, both to be worn in a daily wear modality.

5.2 Purpose of the Study

The purpose of this study is to assess the clinical performance of the TOTAL30 contact lens compared to AOHP. The primary endpoint was selected to address the primary objective of the study. Procedures for measurement of these endpoints were selected based on common practice for these assessments and some novel assessment techniques. The design of this study is justified based upon preclinical and clinical testing, as described within the IFU.

AOHP contact lenses were chosen as the comparator product because both of these lenses have a frequent replacement schedule.

[REDACTED]

[REDACTED]

At the end of the study, a clinical study report [REDACTED] will be prepared in accordance with applicable regulatory requirements and standards. [REDACTED]

[REDACTED]

Alcon reserves the right of prior review of any publication or presentation of information related to the study. [REDACTED]

[REDACTED]

[REDACTED]

[REDACTED]

[REDACTED]

5.3 Risks and Benefits

The clinical investigation process risks are managed through appropriate training and monitoring according to the protocol-specific monitoring plan. Investigational device risks, including risks associated with use of device and methods and procedures for application of device, are defined in the investigator's brochure and/or product labeling and are managed through review of safety assessments outlined in this protocol.

[figure not shown]
Contact lenses may offer improved peripheral vision and the convenience of not wearing spectacles. Material properties and design characteristics of the study contact lenses are features consistent with successful contact lens wear.

TOTAL30 and AOHP contact lenses are commercially available for daily wear use under a frequent replacement wear modality; further details on any known potential risks and benefits can be found in the IFU.

A summary of the known potential risks and benefits associated with the TOTAL30 and AOHP contact lenses can be found in the IFU. There may also be unknown risks to use of the TOTAL30 contact lens. Any risk to subjects in this clinical study will be minimized by compliance with the eligibility criteria and study procedures, clinical oversight and monitoring, and through close supervision by a licensed clinician during exposure to the study lenses. The site personnel will educate subjects on proper hygiene and lens handling, as

well as compliance with the use of contact lenses and lens care according to the protocol. Subjects should be instructed not to wear contact lenses while sleeping or swimming.

The site personnel will also advise the subjects to remove contact lenses and return for prompt follow-up of symptoms, such as ocular discomfort, foreign body sensation, excessive tearing, vision changes, or hyperemia.

6 STUDY OBJECTIVES

[figure not shown]
6.1 Primary Objective(s)

Table 6–1 Primary Objective(s)

Objective(s)	Endpoint(s)
To evaluate visual acuity of the TOTAL30 soft contact lens and the AOHP soft contact lens.	Distance VA with study lenses (OD, OS; logMAR)

6.2 Secondary Objective(s)

Not Applicable.

6.4 Safety Objective(s)

Table 6–3 Safety Objective(s)

Objective(s)	Endpoint(s)
Describe the safety profile of the study products	
• AEs• Biomicroscopy findings• Device deficiencies

7 INVESTIGATIONAL PLAN

7.1 Study Design

[figure not shown]
This is a prospective, randomized, [REDACTED] bilateral crossover, controlled, subject-masked, daily wear clinical study to be conducted at a single site. Eligible habitual soft contact lens wearers will be randomized to 1 of the 2 crossover sequences. Subjects will be masked. A designated study staff member will prepare the contact lenses for dispensing.

Subjects will be expected to participate in a pre-screening and attend 3 office visits: Screen/Baseline/Dispense Lens Pair 1, Follow-up Lens Pair 1/Dispense Lens Pair 2, Follow-up Lens Pair 2/Exit. AOHP will be worn for ~14 days and TOTAL30 will be worn for ~28 days. The total expected duration of participation for each subject is approximately 1.5 months. Subjects will be randomized to wear the assigned product sequence in both eyes, either the test TOTAL30 contact lenses as Pair 1, followed by the comparator AOHP contact lenses as Pair 2, or vice versa. All study contact lenses will be prescribed according to subject's prescription and can be optimized per study lens type, however test and comparator lenses should be dispensed within ± 0.25 D of each other.

Subjects will be expected to wear their study contact lens in a daily wear modality for at least 5 days per week 8 hours a day, over a 14 day (AOHP) or 28 day period (TOTAL30). AOSEPT PLUS with HydraGlyde Cleaning & Disinfecting Solution will be used for daily cleaning and disinfection.

On the day of Visits 2 and 3, subjects will be asked to wear the study lenses at least 6 hours and prior to their study visit. Follow-up visit time to be within ± 2 hours of baseline visit time.

[REDACTED]
[REDACTED]

7.2 Rationale for Study Design

This study design is justified based upon an evaluation of the results of relevant preclinical and clinical testing, as described within the IFU.

The crossover design will ensure that the same subject is exposed to both the test and comparator lens materials [REDACTED]

[REDACTED]. The study will include only those subjects who are current wearers of spherical soft contact lenses in both eyes with at least 3 months wearing experience, with a minimum wearing time of 5 days per week and 8 hours per day. [REDACTED]

Furthermore, the subjects will not be permitted to use lubrication/rewetting drops during the duration of the study as this may confound the primary effectiveness endpoint. The study will exclude any habitual AOHP contact lens wearers in the past 3 months prior to consent in order to reduce potential bias of wearers to their habitual contact lenses. The study will also exclude subjects who wish to wear their contact lenses in monovision modality during the study.

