8 STUDY POPULATION

The study population consists of male and female subjects (aged 18 or over) who are current wearers of spherical soft contact lenses in both eyes with a least 3 months wearing experience, with a minimum wearing time of 5 days per week and 8 hours per day. Subjects who are habitual AOHP contact lens wearers in the past 3 months will be excluded. It is aimed to enroll (consent) approximately 36 subjects at 1 site in the United Kingdom, with a target of 32 completed subjects [REDACTED]

[REDACTED] Estimated time needed to recruit subjects for the study is approximately 5 months; however, unanticipated circumstances may shorten or lengthen this time and would not require amendment of this protocol. Eligible study population will be representative of the study products target population.

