8.1 Inclusion Criteria

Written informed consent must be obtained before any study specific assessment is performed. Upon signing informed consent, the subject is considered enrolled in the study.

[REDACTED]

1. Subjects must be ≥ 18 years of age and have capacity to volunteer.
2. Subjects must be able to understand and must sign an informed consent form (ICF) that has been approved by an Institutional Review Board (IRB/IEC).
3. Current wearers of any commercial spherical soft contact lenses with at least 3 months wearing experience, who would be willing to wear the study lenses for a minimum wearing time of 5 days per week and 8 hours per day.
4. Manifest cylinder ≤ 0.75 D in each eye (based on the ocular refraction).
5. Able to wear contact lenses within a range of sphere power from -1.00 D to -6.00 D (0.25 D steps) and subject willing and able to wear the study lenses for the full duration of the study.
6. Best corrected distance visual acuity better than or equal to 0.10 logMAR in each eye (as determined by manifest refraction at screening).
7. Subjects must be willing to stop wearing their habitual contact lenses for the duration of study participation.
8. Subjects must be willing to NOT use rewetting/lubricating drops at any time during the study

■ [REDACTED]

■ [REDACTED]

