1.2 Study Description

Key components of the study are summarized in Table 1-1.

Table 1–1 Study Description Summary

Study Design	Prospective, randomized,
	bilateral crossover,
	controlled, subject-masked
Study Population	Volunteer subjects aged ≥ 18 years who are any habitual
	spherical soft contact lens wearers, have at least 3 months of
	contact lens wearing experience, and who would be willing to
	wear the study lenses for at least 5 days per week and at least 8
	hours per day.
	Pregnant and breastfeeding women are excluded for this study.
	Target to complete: 32
	Planned to enroll: ~36
Number of Sites	1
	UK
Test Product(s)	TOTAL30 soft contact lenses (TOTAL30)
Commonator Product	ACUVUE OASYS® with HYDRACLEAR PLUS® soft contact
Comparator Product	
D1 1D (; C	lenses (AOHP)
Planned Duration of	Test Product: 28 days
Exposure	Comparator Product: 14 days

[figure not shown]
Visits	Pre-screening
	Visit 1: Screen/Baseline/Dispense Pair 1 [Day 1]
	Visit 2: Follow-up Pair 1/Dispense Pair 2 [AOHP Day 14 (-3/+7
	days); TOTAL30 Day 28 (-3/+7 days)]
	Visit 3: Follow-up Pair 2/Exit [AOHP Day 14 (-3/+7 days);
	TOTAL30 Day 28 (-3/+7 days)]

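### Do Protocol 7.2 and 8 set a stricter habitual-wear requirement than inclusion criterion 3?

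*Protocol*

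**What the plan says.** Five visible places describe who may take part.

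- **Protocol 7.2 (Rationale for Study Design):** "The study will include only those subjects who are current wearers of spherical soft contact lenses in both eyes", with 3 months' experience and "with a minimum wearing time of 5 days per week and 8 hours per day".
- **Protocol 8 (Study Population), opening paragraph:** "current wearers of spherical soft contact lenses in both eyes", then "with a least 3 months wearing experience, with a minimum wearing time of 5 days per week and 8 hours per day".
- **Protocol 8.1, criterion 3:** on lens history it says "Current wearers of any commercial spherical soft contact lenses with at least 3 months wearing experience"; its wearing-time clause, which concerns the study lenses, is "who would be willing to wear the study lenses for a minimum wearing time of 5 days per week and 8 hours per day".
- **Protocol 3 (Protocol Summary):** the subject population row asks for habitual spherical soft lens wear and 3 months' experience; its wearing-time clause is "and who would be willing to wear the study lenses for at least 5 days per week and at least 8 hours per day". The key inclusion row of the same table repeats criterion 3.
- **SAP 1.2, Table 1-1:** the experience and willingness conditions appear together, as "contact lens wearing experience, and who would be willing to"; the same minimum time follows, again for the study lenses.

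The first two attach the 5-day, 8-hour figures to existing wear and require it in both eyes. The other three attach the figures to wear of the study lenses and do not mention both eyes.

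**The concern.** Section 7.2 is worded as a restriction, and Section 8 repeats it, so this is not one stray phrase. The neighbouring statements in 7.2 on rewetting drops, habitual AOHP wear and monovision each have a visible counterpart (inclusion criterion 8, exclusions 14 and 13). The habitual-time and both-eyes conditions have none.

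If the narrative counts as a requirement, a subject correctly admitted under criterion 3 could be logged as a protocol deviation. Section 14 requires deviations to be recorded and prohibits waivers. Section 12.1 settles evaluability from a separate Deviations and Evaluability Plan, and 12.5 speaks of data in evaluable subjects and eyes. Someone could therefore be dropped from the primary visual acuity summary for missing a condition the site was never asked to check. The study report could also describe the sample by a habitual wearing time that nobody had to meet.

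**Working it through.** The plan states no figure to reproduce. Section 12.7 and SAP 7 give no sample size calculation, and Section 12.4.1.1 and SAP 4.2 set no hypothesis. The check is therefore a reading of the passages in sequence.

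**1. Who passes one text and fails the other?**

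| Person (at least 3 months' experience, willing to follow the study schedule) | Criterion 3, Summary, SAP Table 1-1 | Protocol 7.2 and 8 |
|---|---|---|
| Wears lenses in both eyes, 5 days, 8 hours | in | in |
| Wears lenses in both eyes, 4 days, 8 hours | in | out |
| Wears a lens in one eye only | in on this wording | out |

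So the difference is real on the visible text.

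**2. Which text decides enrolment?** Section 9.3 has the site randomize only after it has confirmed the eligibility criteria. Those are the numbered lists in 8.1 and 8.2. Section 7.2 explains the design, and the opening of Section 8 introduces the lists. A site working through the checklist applies criterion 3.

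**3. Is the list fully visible?** No. In 8.1, text before criterion 1 and two items after criterion 8 are blacked out. In 8.2, item 9 is absent. In 7.2, text directly after the wearing-time sentence is blacked out. A withheld item could carry either condition, and 7.2 and 8 would then be accurate summaries of the whole list. The Protocol Summary gives only key criteria and refers to 8.1 for the rest, so its silence on both eyes proves little.

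**4. How much room is there for a one-eye wearer?** Very little. Lenses are worn bilaterally (7.1), the power range runs from -1.00 to -6.00 D, the cylinder and best-corrected acuity limits apply to each eye (8.1), monovision is excluded (8.2), and a subject who cannot be fitted with either study lens must exit (Section 10). None of these formally requires habitual wear in both eyes, but together they nearly close the third row of the table.

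**5. Would an affected subject leave the analysis?** Section 12.4 and SAP 4 name the Safety Analysis Set for effectiveness, though words around that statement are withheld. Section 12.2.1 and SAP 2.1 build that set from exposure to a study lens, in a sentence that also runs into withheld text. It is the only analysis set visible in either document. As far as it can be read, entry depends on exposure and not on compliance with a population description.

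**6. Would it distort a lens comparison?** Each subject is meant to wear both lenses (7.1). A completer with lower habitual wear contributes to both lens summaries, and leaving that person out would remove data from both. Section 12.1 also requires evaluability to be settled before the masked sequence code is broken.

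**7. Size.** The documents give no count of subjects who meet criterion 3 but not the narrative, and no acuity difference for them. Any shift in mean logMAR would rest on two invented inputs, so none is offered.

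**The case for a change.** The strongest reply is that the duties in Section 14 cover the whole protocol and not only 8.1 and 8.2. A monitor could cite the restriction in 7.2, repeated in 8, and log a deviation. Section 12.5 and SAP 4 both limit the data to evaluable subjects and eyes, which leaves some room for exclusion despite an exposure-based set. Even if a withheld item supplies the conditions, criterion 3 and the narrative would still read differently. In addition, the habitual-lens row in Table 3-1 names brand, power and lens care but not wearing time, so the narrative condition has no visible check.

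Much of this stands as description: the texts do differ, and a careful editor would align them. The harm is not shown. It needs the Deviations and Evaluability Plan, which is not among the documents, to treat introductory prose as an eligibility rule over the numbered criteria, and nothing visible suggests that it does. The missing check on habitual wearing time points the other way: it fits a condition that sites were not meant to apply. Section 10.2.2 also has habitual lens information recorded at Visit 1, so wearing time may well be in source. If anyone were excluded, SAP 3 plans a listing of subjects left out of the analysis set, so the exclusion would be visible.

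**Conclusion.** The inconsistency is genuine but clerical. Narrative text in Protocol 7.2 and 8 describes existing wear, while the text that governs enrolment asks for willingness to wear the study lenses. Aligning the two would not alter whom the site enrols, which data are summarised or what a descriptive study without hypotheses can conclude. On the visible text the effect on the primary endpoint is nil.

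This rests on three assumptions: that the numbered criteria govern enrolment, as Section 9.3 indicates; that the withheld parts of the Safety Analysis Set wording add no eligibility condition; and that the Deviations and Evaluability Plan refers to the numbered criteria. The first is well supported by the documents, and the other two cannot be checked from them. The residual risk is how the report words its population. A report writer would ordinarily describe the sample by the criteria actually applied, and no amendment is needed for that.
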